Neuropsychological and Neurological Testing: Our *primary cognitive outcome* will be the total score on the Mattis Dementia Rating Scale (MDRS)⁹⁹ which measures multiple cognitive domains and is validated in PD.¹⁰⁰ An important secondary question is whether connectivity in specific networks are associated with domain specific deficits. We will thus perform tests in the following domains: 1) Executive function (Trails B, Verbal Fluency, Stroop)¹⁰¹; 2) Memory (Hopkins Verbal Learning Test)¹⁰²; 3) Language (Boston Naming Test)¹⁰³; 4) Attention (Brief Test of Attention)¹⁰⁴; and 5) Visuospatial (Judgement of Line Orientation)¹⁰⁵. Finally, we will perform the Unified Parkinson's Disease Rating motor section¹⁰⁶ to use as a covariate in models for disease severity.

MRI:

MRI scans will be acquired using a G.E. 3.0 T Signa, whole body magnet with an Excite upgrade and 8-channel head coil using a 3-D, extended dynamic range, inversion recovery SPGR ASSET parallel imaging sequence with excellent gray/white contrast. The T1-weighted series will consist of .94 mm thick coronal images and can be acquired in 9 minutes. MRI images will be aligned with MEG using SPM8 software.¹⁰⁷

The following additional sequences will be optional for participants and add approximately one hour to the MRI scan but do not add risk and the patient does not have to do anything except lie still.

Participants will be informed that these scans are not essential to the study and that we can stop scanning at any point should they become uncomfortable.

Diffusion tensor imaging (DTI) is a MRI scanning technique that enables one to assess the diffusion of water in brain tissue. The risks to subjects are identical to those in standard T1-weighted MRI scanning (i.e., no more than minimal risk). The purpose of DTI is to better quantify the white matter, or axon segments, of the brain.

¹H-MRS can be used to quantify a range of brain metabolites, including n-acetylaspartate and glutamine/glutamate, markers of neuronal density and/or neuronal integrity. The MRS scan will allow us to crudely quantify neuronal integrity within the motor cortex. We will focus a single voxel of interest on the left prefrontal cortex because whole brain human MRS is prohibitively time-consuming and impractical. We will test the hypothesis that changes in connectivity are correlated to decreased levels of glutamate and GABA within the frontal cortex in persons with Parkinson's disease.

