For purposes of comparison to MEG resting state, echo-planar imaging-gradient recalled echo (EPI-GRE) data normally acquired during functional MRI scanning (fMRI) will be acquired during the MRI session. Subjects will simply rest in the prone position with their eyes open for 2 minutes and closed for 2 minutes. The 10 minute baseline MRI scan will allow us to compare the generators of resting state MEG gamma-band to resting state activation in fMRI.

The total MRI procedure, if patients consent to the additional sequences, will last approximately 70 minutes and will begin with the anatomical portion. In case the study subjects feel any discomfort anytime after this first acquisition, they will be freed of terminating the additional scans without being disqualified from the study.

MEG Data Collection: Magnetic field data will be recorded using a whole head neuromagnetometer (4D Neuroimaging) with an array of 248 sensors at rest with eyes open for 2 minutes and closed for 2 minutes at a 678 Hz sampling rate. Data will be processed offline using a 0.1-100 Hz band pass filter. Data will be manually examined and five 6-second artifact free epochs for both eye-open and closed conditions will be selected for further analyses. Artifact correction if needed will be performed using independent components analysis.¹⁰⁸ Sensors will be realigned to a common sensor array to allow group level analysis in a shared brain space.¹⁰⁹

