AIM 1 Statistical Analysis and Sample Size: To address our primary research question, Spearman correlations will be used to identify frequency spectra small-worldness measures associated with the MDRS in eyes-closed data with a false detection rate set at 0.05 to handle the issue of multiple comparisons. We will then use linear regression to determine whether small-worldness in these specified frequency bands remain associated with the MDRS when controlling for each other as well as other important covariates, namely age and motor severity. A *sample size* of 45 (allowing for 5 drop-outs and/or unusable data-sets from the original 50) will allow us to detect correlations of 0.18 or higher between our MEG features and MDRS with 80% power 0.05 significance. This is comparable to correlations of 0.19 and higher seen in other resting state MEG studies of cognition.¹¹⁵ Planned secondary analyses will parallel our primary analysis to determine whether global efficiency, nodal efficiency or degree distribution are significantly associated with MDRS in linear regression models. Exploratory analyses will assess reactivity of these measures between eyes open and closed conditions and assess whether domain specific neuropsychological test scores are associated with connectivity within networks defined by domain related nodes (e.g. occipital nodes and visuospatial tests).

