in small-worldness or other MEG features. With a total *sample size* of 50 (25 per group allowing for 5 drop-outs from original 55) we will be able to determine a between group difference of 10 points on the MDRS (assuming a SD of 13 as per prior trials and an effect size 0.77)¹²⁴ with 80% power and 0.05 significance. This sample size is comparable to prior PDD studies. For example, a study of rivastigmine in PDD detected significant change on the Mattis with only 28 subjects.¹²⁴

Exploratory Aim Statistical Analyses and Sample Size: We will address our exploratory research questions by looking at Spearman correlations or linear models of MEG and MRI measures. Power considerations are similar as for Aim 1 with detection of correlations of 0.18 or higher between our MEG and MRI features with 80% power 0.05 significance.

G. Summarize Knowledge to be Gained:

PD is the second most common neurodegenerative disease, affecting over one million Americans and dementia is the most common cause of nursing home placement in this population.^{53, 54} Our understanding of the neurobiological mechanisms of cognitive dysfunction in PD are limited and we do not have efficacious treatments. This research will address this significant public health issue in three major ways: 1) Identify abnormalities in cortical connectivity associated with cognitive dysfunction in PD; 2) Develop a MEG biomarker for cognitive dysfunction in PD; and 3) Evaluate the potential for TMS to induce durable changes in PD cognitive function and connectivity. Given the burden of dementia in this population, we feel that the minimal risks involved are justified both to individual PD and PD-MCI subjects, the larger population of PD and PD-MCI patients, and to society as a whole. Recent TMS studies using published safety guidelines suggest that the risks of TMS may be even lower than previously described. Even using conservative estimates and anticipating some discomfort from prolonged sitting and cognitive testing, we argue that this research is imperative to advance this field and ultimately to provide relief to these patients and their caregivers.

H. References:

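### The Exploratory Aim borrows Aim 1's power statement, but its MRI data come from optional scans, so the number analysed is unspecified, and 80% power for r = 0.18 is not reached at any size the enrolment allows

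*Combined protocol and SAP*

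**What the plan says.** Section IV.F, under the Exploratory Aim, plans to answer its questions by "looking at Spearman correlations or linear models of MEG and MRI measures". It gives no sample size. On power it says "Power considerations are similar as for Aim 1" and then repeats Aim 1's target for the MEG-MRI pairs: r = 0.18, power 80%, significance level 0.05.

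The Aim 1 paragraph of the same section claims that 45 subjects suffice to "detect correlations of 0.18 or higher between our MEG features and MDRS with 80% power 0.05 significance". The 45 is reached by "allowing for 5 drop-outs and/or unusable data-sets from the original 50". The data Aim 1 needs are resting MEG and the MDRS total score.

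The Exploratory Aim (Section I) needs white-matter, GABA and resting-state measures. Section IV.A, under MRI, obtains these from DTI, proton spectroscopy and echo-planar imaging, and states: "The following additional sequences will be optional for participants and add approximately one hour to the MRI scan". Participants are to be told that scanning can stop at any time. Those who become uncomfortable after the anatomical scan are not lost to the trial: "they will be freed of terminating the additional scans without being disqualified from the study". The Schedule of Procedures in Section IV.C also lists the functional scans as optional.

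Section IV.B plans to enrol 25 PD subjects without cognitive impairment and 55 with MCI or mild dementia, 80 in all. Section IV.D plans MEG and MRI for both the PD and the PD-MCI subjects.

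**The concern.** A power statement belongs to a particular analysis set. Aim 1's allowance of 5 covers drop-out and unusable data in a cohort of 50 whose required data are MEG and MDRS. A participant who declines the optional hour, or stops during it, still counts in full for Aim 1 but contributes nothing to the exploratory correlations that use the missing sequence. Aim 1's allowance cannot absorb that loss. The plan gives no expected uptake, no target number per sequence and no definition of who enters these analyses.

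The borrowed detectable correlation also has to be right for the sentence to inform anyone, and it is not. A reader who met a null MEG-GABA or MEG-white matter result could take it as evidence against correlations of about 0.2, which the study would have had little chance of detecting. The stakes are modest: the aim is labelled exploratory, and no primary or secondary conclusion depends on it.

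**Working it through.** **Inputs from the documents.** Aim 1: 50 enrolled, 45 analysable, a loss of 5/50 = 10%. Stated target: r = 0.18, 80% power, significance 0.05, sidedness not given. Enrolment: 25 + 55 = 80.

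**Inputs assumed.** The documents give no completion rate for the optional sequences; 60% to 80% is used for illustration. MEG loss among the 80 is taken at Aim 1's 10%, leaving 80 × 0.90 = 72.

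**Formulas** (Fisher z, one correlation, two-sided 0.05):

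- Power = Φ(atanh(r)·√(n − 3) − 1.960), plus a negligible opposite tail.
- Detectable r at 80% power = tanh((1.960 + 0.842)/√(n − 3)).
- Required n = ((1.960 + 0.842)/atanh(r))² + 3.

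**Step 1: the plan's own figure.** With r = 0.18, atanh(r) = 0.182.

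- n = 45: 0.182 × √42 = 1.179, and 1.179 − 1.960 = −0.781, so power is 22%, not 80%.
- Detectable r at n = 45: tanh(2.802/6.481) = 0.41.
- Required n for r = 0.18: (2.802/0.182)² + 3, which gives 240.

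The figure does not reproduce. A one-sided test gives 32% power, a detectable r of 0.37 and a required n of 190. A Spearman variance factor of 1.06 (two-sided) gives 21% power and a detectable r of 0.42. For a one-predictor regression at n = 45, the f² detectable with 80% power is 0.183, so 0.18 may be an f² labelled as a correlation. That is an inference; the plan does not say so.

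**Step 2: how many could be analysed.**

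| Pool with usable MEG | Completion (assumed) | n |
|---|---|---|
| 45 (Aim 1 only) | 60% | 27 |
| 45 (Aim 1 only) | 80% | 36 |
| 72 (all enrolled) | 60% | 43 |
| 72 (all enrolled) | 80% | 58 |
| 72 (all enrolled) | 100% | 72 |

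From 72, reaching 45 takes 45/72 = 62.5% completion.

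**Step 3: what those numbers deliver.**

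| n | Power for r = 0.18 | r detectable with 80% power |
|---|---|---|
| 27 | 14.5% | 0.52 |
| 36 | 18% | 0.45 |
| 45 | 22% | 0.41 |
| 58 | 27% | 0.36 |
| 72 | 33% | 0.33 |
| 80 | 36% | 0.31 |

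Even at the recruitment ceiling of 150 in Section IV.B, power for r = 0.18 is 60%.

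**The case against.** The strongest reply is that nothing confines this aim to Aim 1's cohort. MEG and MRI are planned for all 80, so optional scanning need not push the number below 45. With 60% to 80% completion among 72 usable subjects, n is 43 to 58. For r = 0.405, close to what 45 subjects can detect, power is then about 78% to 89%, against 79.5% at n = 45. On sample size alone, treating the aim as similar to Aim 1 could be fair or even conservative. This stands, and it rules out two stronger readings.

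A reader might infer that each sequence must have fewer than 45 subjects. The documents do not say so; that follows only if the pool is Aim 1's cohort.

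A reader might also infer a power loss of 10 to 24 points, by applying 80% and 60% completion to the 45 (69% and 56% power at r = 0.405, against 79.5%). That uses the smaller pool and an assumed rate, so it is not a finding about this plan.

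It is equally tempting to say that later sequences will be lost more often. Section IV.A fixes only that the anatomical scan comes first. It gives no completion data, so the most that can be said is that completion may differ by sequence.

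Two further replies carry less weight. Section IV.B allows recruitment of up to 150 to cover screen failures, drop-out and unusable data, but does not mention refusal of the optional scans. It is also true that an exploratory aim needs no power claim. This plan nevertheless makes one, with a correlation, a power and a significance level.

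Finally, one can say that the real fault is the 0.18. It is the larger error, but correcting it in Aim 1 alone would leave the exploratory text pointing to a count of subjects that is not its own.

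**Conclusion.** The point holds in limited form. The Exploratory Aim's power is borrowed from an analysis set defined by MEG and MDRS, while its own data depend on optional scans. The number analysed is therefore unspecified, may vary by sequence, and may be below, equal to or above 45. The direction of the difference cannot be settled from the documents.

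The stated 80% power for r = 0.18 is wrong over the whole range: about 22% at n = 45 and 36% at n = 80. This part needs no assumption about completion. It rests on the Fisher z approximation with a two-sided 0.05 test, and a one-sided or rank-based calculation does not rescue it. The 27, 36, 58 and 72 completers are illustrations built on an assumed completion rate and, for 58 and 72, an assumed 10% MEG loss. The matter is minor, because the aim is exploratory.

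**What to change.** Replace the power sentence under the Exploratory Aim with three elements:

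- **Analysis set.** Each MEG-MRI analysis uses all enrolled subjects, up to 80, who have usable baseline MEG and completed the sequence concerned.
- **Precision.** Give the correlation detectable with 80% power at two-sided 0.05 over a range of completers: 0.52 at 27, 0.45 at 36, 0.41 at 45, 0.36 at 58 and 0.33 at 72. Label the completion rate behind the range as an assumption, and remove the 0.18.
- **Reporting.** For each sequence, report the number analysed and a 95% confidence interval for the correlation.

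The cost is a few sentences of protocol text and a less favourable power statement. No scans or patients are added.
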